- To characterize HPV and HIV knowledge and risk and sexual behaviors in the study cohort populations.

Eligibility:

Individual Cohorts

- Cohort 1: HIV-positive, CD4 cell count ≥ 350 cells/mm³, HIV-1 RNA level by RT PCR $\leq 20,000$ copies/ml, on stable HAART regimen for ≥ 6 months.
- Cohort 2: HIV-infected, CD4 cell count ≥ 500 cells/mm³, HIV-1 RNA level by RT PCR $\leq 20,000$ copies/ml, on no antiretroviral treatment.
- Cohort 3: healthy, HIV-negative controls

All Cohorts

- Females and males age 12 to 26 years
- Patients must have a hemoglobin ≥ 10.0 gm/dL, neutrophil count (ANC) $\geq 1500/\text{mm}^3$, platelet count $\geq 75,000/\text{mm}^3$ and PT or PTT $\leq 1.5X$ ULN (with the exception of patients with known clotting disorders or lupus anticoagulant); SGPT/SGOT $\leq 2/5X$ ULN, total bilirubin $\leq 1.5X$ ULN unless attributable to protease inhibitor therapy.

- Patients must test negative for hepatitis B virus and hepatitis C virus, unless the result is consistent with prior vaccination or prior infection with full recovery.
- No use of investigational agents within 4 weeks of study enrollment or use of immunosuppressive or immunomodulating agents within 8 weeks of study entry.

Study Design:

- This is a non-randomized, prospective, phase I study of quadrivalent human papillomavirus (types 6, 11, 16, 18) recombinant vaccine.
- The study includes 3 cohorts of pre-adolescents, adolescents and young adults 12-26 years of age as outlined under Eligibility Criteria. Each cohort will enroll 35 patients.
- All study subjects will receive three doses of HPV vaccine at 0, 2 and 6 months administered IM.
- Study participants will be monitored at months 0, 1, 2, 3, 6, 7 and 12 (\pm 2 weeks for each visit) and every 6 months (\pm 30 days) thereafter for 48 months total.

TABLE OF CONTENTS

PRECIS	2
TABLE OF CONTENTS	4
1 INTRODUCTION	7
1.1 Study Objectives	7
1.2 Background and Rationale.....	7
1.2.1 Human Papillomavirus (HPV) Infection	7
1.2.2 HPV Infection in Children.....	9
1.2.3 Adolescent Sexual Behavior and HPV Infection.....	10
1.2.4 HIV Infection and HPV Co-Morbidity	11
1.2.5 Quadrivalent Human Papillomavirus (types 6, 11, 16, 18) Recombinant Vaccine	13
1.2.6 Rationale for Study Cohort Population.....	15
2 ELIGIBILITY ASSESSMENT AND ENROLLMENT.....	16
2.1 Eligibility Criteria	16
2.1.1 Cohort 1 Inclusion and Exclusion Eligibility Criteria	16
2.1.2 Cohort 2 Inclusion and Exclusion Eligibility Criteria	17

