1.2.6 Rationale for Study Cohort Population

This study will be conducted in both HIV-infected females and males 12-26 years of age. Since the risk of HPV acquisition is intensified during adolescence and young adulthood because of risk-taking and exploratory behaviors and because of the well-documented co-morbidities associated with sexually acquired HPV in individuals with HIV infection, both males and females are included in the study. It is anticipated that Cohort 1 will be comprised primarily (but not exclusively) of sexually naïve pre-adolescents and adolescents infected with HIV vertically or by transfusion early in life that have experienced successful immune reconstitution and viral load reduction on HAART therapy (i.e. CD4 count ≥ 350 cells/mm³ and HIV-1 RNA levels $\leq 20,000$ copies/ml). This population represents an ideal one to investigate vaccine immunogenicity given the high likelihood of HPV acquisition following the initiation of sexually activity.

It is anticipated that Cohort 2 will be comprised primarily (but not exclusively) of adolescents and young adults with sexually acquired HIV infection that have no current indication for HAART therapy according to current USPHS Treatment Guidelines (i.e. CD4 count ≥ 500 cells/mm³ and HIV-1 RNA levels $\leq 20,000$ copies/ml).⁹⁸ These individuals represent a unique population to assess HPV vaccine immunogenicity and safety that parallels populations in developing countries with little or no access to antiretroviral treatment where there is a high burden of prevalent HPV and HIV disease. Both Cohorts 1 and 2 will permit assessment of whether HPV vaccination is associated with alterations in HIV-1 RNA levels and if observed, whether alterations are mitigated in the presence of HAART. In addition, both HIV-infected cohorts will allow investigation of the impact of CD4 count and HIV-1 RNA levels on HPV vaccine immunogenicity.

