2 ELIGIBILITY ASSESSMENT AND ENROLLMENT

2.1 ELIGIBILITY CRITERIA

2.1.1 Cohort 1 Inclusion and Exclusion Eligibility Criteria

Inclusion Criteria

- 2.1.1.1 Age 12 to 26 years
- 2.1.1.2 Females and males
- 2.1.1.3 HIV-positive
- 2.1.1.4 CD4 cell count and HIV-1 RNA level parameters
 - 2.1.1.4.1 CD4 cell count \geq 350 cells/mm³
 - 2.1.1.4.2 HIV-1 RNA level by RT PCR \leq 20,000 copies/ml
- 2.1.1.5 On stable HAART regimen for > 6 months with CD4 and viral load parameters as outlined in 2.1.1.4
- 2.1.1.6 Patients > 18 years willing to provide informed consent or parent/guardian willing to provide informed consent for minor children <18 years of age.
- 2.1.1.7 Informed assent for patients 12-17 years of age (Optional at the discretion of the Principal Investigator and Parent/Guardian based on maturity level of minor)
- 2.1.1.8 Willing to use acceptable forms of contraception, if applicable, or abstinence to prevent pregnancy.

Exclusion Criteria

- 2.1.1.9 Any of the following hematologic abnormalities
 - 2.1.1.9.1 Hemoglobin < 10.0 g/dL
 - 2.1.1.9.2 Neutrophil count < 1500/mm³
 - 2.1.1.9.3 Platelet count < 75,000/mm³
 - 2.1.1.9.4 PT or PTT \geq 1.5X ULN (with the exception of patients with known clotting disorders or known lupus anticoagulant).
- 2.1.1.10 Any of the following hepatic abnormalities

- 2.1.1.10.1 ALT/SGPT and/or AST/SGOT > 2.5X ULN
- 2.1.1.10.2 Total bilirubin > 1.5X ULN unless attributable to protease inhibitor therapy.
- 2.1.1.11 Positive tests (antibody and/or antigen) for hepatitis B and hepatitis C viruses, unless the result is consistent with prior vaccination or prior infection with full recovery.
- 2.1.1.12 Acute infection requiring therapy at time of enrollment. Participants may be eligible for study after being on stable and appropriate anti-infective therapy.
- 2.1.1.13 Chemotherapy for active cancer.
- 2.1.1.14 Documented history of non-adherence to antiretroviral treatment regimen within 12 months of study entry.
- 2.1.1.15 Pregnancy or breastfeeding.
- 2.1.1.16 Use of immunosuppressive or immunomodulating agents within 8 weeks of study enrollment. Note: patients receiving oral corticosteroids for management of asthma or contact hypersensitivity for < 14 days in duration will be allowed to enroll as long as it has been > 30 days since oral corticosteroid administration.
- 2.1.1.17 Known immediate hypersensitivity to yeast or any of the vaccine components.

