Timepoints for HIV-1 RNA Level Analysis: Comparison between Recipients in HIV-Infected Cohorts 1 and 2:

- Timepoint 1 Day 1 vs. Day 3 or Day 7 (immediately s/p vaccination) (*primary*)
- Timepoint 2 Day 1 vs. mos 1 (1mos s/p 1 vaccination)
- Timepoint 3 Day 1 vs. mos 3 (1mos s/p 2 vaccinations)
- Timepoint 4 Day 1 vs. mos 7 (1mos s/p 3 vaccinations)
- Timepoint 5 Day 1 vs. mos 12 (6mos s/p 3 vaccinations)

Within each cohort, the change in \log_{10} HIV-1 RNA levels will be determined between day 1 and day 7 and will be evaluated to see if the values at the two time points are not statistically different from one another. HIV-1 RNA levels below the lower limits of detection (50 copies/ml) will be expressed as 1.69 \log_{10} on a logarithmic scale equivalent to 49 copies/ml. With a minimum of 27 patients in each cohort of HIV-infected individuals, there is at least 95% power to detect a change from day 1 to day 7 with an effect size of 1 SD and a 0.025 two-sided alpha level test (0.05/2cohorts) after allowing for a Bonferroni adjustment.

In addition, as a secondary evaluation, comparison of changes in HIV-1 RNA levels will also be done among the two cohorts from day 1 to day 7, and months 1, 3, 7 and 12 in order to assess if the change in level may have some association with the cohort in which the patient is enrolled. This evaluation will be considered exploratory for all comparisons and timepoints.

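### The 1 SD power figure in section 6.3 is correct, but a mean-change test in a largely suppressed Cohort 1 is insensitive to rebound in a few patients, and no analysis there bounds rebound within a cohort

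*Combined protocol and SAP*

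**What the plan says.** Section 6.3 (Primary Virologic Safety Analysis) plans, within each HIV-infected cohort, a day 1 to day 7 comparison of log10 HIV-1 RNA that "will be evaluated to see if the values at the two time points are not statistically different from one another". It gives a floor rule: "HIV-1 RNA levels below the lower limits of detection (50 copies/ml) will be expressed as 1.69" log10, the equivalent of 49 copies/ml. The next sentence gives the power: "With a minimum of 27 patients in each cohort of HIV-infected individuals, there is at least 95% power to detect a change". The effect size there is 1 SD, and the two-sided alpha is 0.025, which is 0.05 divided over the two cohorts. The section names no test, gives no SD in log10 units, states no expected share of patients below 50 copies/ml, and does not discuss tied zero changes.

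The Precis sets the cohort size: "Each cohort will enroll 35 patients". Cohort 1 is on stable HAART, and section 1.2.6 expects it to consist mainly of patients who have "experienced successful immune reconstitution and viral load reduction on HAART therapy". That section defines the viral load part as at most 20,000 copies/ml, and the entry criterion in 2.1.1 uses the same ceiling. Suppression below 50 is not required.

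Section 6.3 also contains a responder analysis, which it ranks as the most important. This takes the fraction with a rise of at least 0.5 log10, assumed to be no more than 5%, and compares it between Cohorts 1 and 2 within a 10% margin.

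**The concern.** In patients on effective HAART, the virologic harm to look for is loss of suppression in a few individuals, not a shift of the whole cohort. A mean-change test handles that pattern badly. Patients at the floor at both visits add zeros that pull the mean down, and larger rises in the few rebounders inflate the SD along with the mean.

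The plan looks for absence of a significant difference under a power statement of at least 95%. A reader of the final report could take a non-significant Cohort 1 result as well-powered evidence that vaccination did not alter HIV-1 RNA in treated patients. Whether it does so is a stated objective (section 1.1). The responder analysis does not close this gap. It asks only whether the two cohorts differ, so similar fractions in both satisfy its equivalence hypothesis however high they are.

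**Working it through.** **Inputs.** From 6.3: n=27 minimum, 1 SD effect, two-sided alpha 0.025, floor 1.69 log10, assumed responder share 5%. From the Precis: n=35. Inferred: a paired t-test, because the effect is in SD units. Assumed: the share of Cohort 1 below 50 copies/ml at both visits.

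**Step 1: the plan's own figure.** Paired t-test, noncentrality 1 × √27, 26 df, two-sided 0.025: power 99.65% (n=35: 99.97%). The printed figure of at least 95% holds.

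**Step 2: limiting case.** Let k of n patients rise by the same amount d and let the rest change by exactly 0. The mean change is kd/n and the sample variance is d²k(n−k)/[n(n−1)], so

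t = √[k(n−1)/(n−k)].

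The rise d cancels. Unequal rises give a smaller t.

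| n | critical t | k=4 | k=5 |
|---|---|---|---|
| 35 | 2.345 | √(4×34/31) = 2.094, p=0.044 | √(5×34/30) = 2.380, p=0.023 |
| 27 | 2.379 | √(4×26/23) = 2.126, p=0.043 | √(5×26/22) = 2.431, p=0.022 |

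At least 5 rebounders are needed at either size: 5/35 = 14% or 5/27 = 19%. With an exact signed-rank or sign test that drops zeros, the smallest attainable p is 2 × 0.5^k: 0.031 for k=6 and 0.016 for k=7. At least 7 would then be needed.

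**Step 3: upper bound on power in that case.** This is P(X ≥ 5) for X binomial.

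| true rebound fraction | n=27 | n=35 |
|---|---|---|
| 5% (the plan's assumed share) | 1.0% | 2.9% |
| 10% | 12.7% | 26.9% |
| 20% | 65.2% | 85.7% |

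**Step 4: what 1 SD means here.** If a fraction q rises equally and the rest stay at zero, the standardised effect is √[q/(1−q)], which equals 1 only at q = 0.5. Unequal rises need a larger q. At q = 0.5, P(X ≥ 5) is 99.98% at n=27, so the zeros do not undermine the power at a true 1 SD effect. They make 1 SD a very large effect: 4 of 35 rebounding is at most 2.094/√35 = 0.35 SD.

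**Step 5: relaxing the assumption.** Four rebounders of 35, with 25, 20, 15 or 0 of the other 31 at the floor and the rest varying around zero with SD 0.15 or 0.30 log10 (20,000 simulated trials each). The chance of significance was:

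- 9–19% for a 0.5 log10 rise
- 9–19% for 1.0 log10
- 1–17% for 2.0 log10
- 0–15% for 3.0 log10

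Even with nobody else at the floor it stayed below 20%. The low sensitivity therefore comes mainly from testing a mean; a fully suppressed remainder takes it to zero.

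**The case against.** Several points on the other side stand.

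- A reader might infer that the printed power is wrong, or that the floor lowers it. It does not. The natural reading of 1 SD is the SD of change in the whole cohort, zeros included, and for that effect the figure is correct. Lower powers arise only if 1 SD is redefined as the shift among patients with measurable virus, which the plan does not say.
- A reader might also infer that rebound in 4 of 35 can never be significant. That needs all 31 others below 50 copies/ml at both visits. The documents neither require nor predict this, and entry allows up to 20,000 copies/ml.
- The paired t-test is an inference, and the cut-off of 5 depends on it.
- The responder analysis does count every rise of 0.5 log10 or more, so per-cohort counts must be produced anyway. What is missing is a within-cohort statement of uncertainty.
- The accrual stopping rule (6.7) offers some protection. However, its virologic trigger in 3.7 is a confirmed rise above 100,000 copies/ml, so lower-level rebound does not trip it.
- A binomial summary is not a sharper alarm. Against the plan's 5%, the exact one-sided p is 0.096 for 4/35 and 0.029 for 5/35, so 6/35 would be needed at 0.025. Its value is that it bounds the rebound rate.

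**Conclusion.** The concern holds in a limited form. The power statement is true but uninformative about the event that matters in a treated cohort, because 1 SD is not linked to a log10 change or a rebound fraction. In a largely suppressed Cohort 1 that effect is out of reach unless about half the cohort rebounds.

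The strict result, no significance with 4 or fewer rebounders of 35 or of 27, rests on two assumptions: a paired t-test at two-sided 0.025, and all other patients below 50 copies/ml at both visits. Without the second assumption, detection of 4 rebounders was still under 20% in every scenario run.

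The documents do not support saying that the 95% is an error or that such rebound is undetectable in all circumstances. They do support saying that a non-significant mean change in Cohort 1 is weak evidence of no harm, and that nothing in 6.3 bounds the rebound rate within either cohort.

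**What to change.** In section 6.3:

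1. For each HIV-infected cohort, report the number and percent with a rise of at least 0.5 log10, using the planned floor of 1.69, with an exact binomial confidence interval. Report separately the number going from below 50 copies/ml to detectable.
2. State that a non-significant mean-change test in Cohort 1 will not be read as evidence of no change.
3. State that the 1 SD power figure is a cohort-level effect, which a largely suppressed cohort cannot reach unless about half of it rebounds. Name the test and give the expected suppressed share.

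The cost is some wording and one table, using a threshold already in 6.3. The downside is that the Cohort 1 conclusion then rests on a fairly wide interval: the one-sided 95% upper limit is 8.2% for 0/35 (1 − 0.05^(1/35)) and 16.9% for 2/35.

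One dependency needs separate attention. Section 6.3 analyses days 1, 3 and 7, but Appendix 2A schedules no HIV-1 RNA sample on those days: it shows screening and then month 1 onward. The two must be reconciled before it can be assumed that the data for this comparison exist.

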6.4 SECONDARY ANALYSES

Examination of fold increase in HPV titer and correlation with baseline CD4 count and viral load will be treated as a secondary analysis that will primarily be descriptive/exploratory. With 35 vaccine recipients within each cohort, there will be approximately 87% power to detect between a 0.80 correlation coefficient and a 0.50 correlation coefficient with a 2-sided .05 alpha level test.

6.5 ADDITIONAL STATISTICAL ANALYSES BY MERCK

Biostatisticians from Merck will assess geometric mean titers at months 1, 3, 7 (± 2 weeks), 12, 24, 36, and 48 (± 30 days) for HIV-infected Cohorts 1 and 2 individually and collectively, as well as HIV-negative Cohort 3, in comparison with geometric mean titers at these timepoints documented in vaccine recipients in their clinical approval and licensing studies.

6.6 DESCRIPTIVE ANALYSES

Analyses of HPV/HIV knowledge and risk behavior survey responses will be descriptive and exploratory for all study cohorts. No statistical comparisons between cohorts are planned. . Study investigators will not have access to raw survey response data and will not be able to link survey responses to study participants.

6.7 ACCRUAL STOPPING RULE

Accrual to the HIV-infected cohorts (Cohort 1 and Cohort 2) will be halted if 3 or more patients within a given cohort or 5 or more total patients between the two cohorts are removed from the study before month 12 for a decline in CD4 count (3.9.7) and/or an increase in HIV-1 RNA levels (3.9.8) as outlined in section 3.9 Off-Treatment/Off-Study Criteria. Occurrence of these events prior to study month 12 would be suggestive of potential excess virologic safety risk possibly related to HPV vaccination, while their occurrence after study month 12 is most likely to be due to the emergence of antiretroviral resistance (Cohort 1 on HAART) or the natural history of the disease within an individual (Cohort 2 on no treatment). Study month 12 was the cutoff chosen for this stopping rule as it includes 12 months of observation following the first HPV vaccination and 6 months of observation following completion of the vaccination series (3 vaccine doses) at study month 6. In the event that accrual to the study is halted, the IRB will be consulted to determine whether the halt on enrollment should be permanent or can be addressed through an amendment to the protocol.

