3.7 OFF TREATMENT AND OFF STUDY CRITERIA

- Off Treatment- Any Grade III or higher toxicity possibly or probably related to vaccine that does not resolve to baseline within 4 weeks with appropriate intervention.
- Off Treatment- Any Grade IV toxicity unrelated to vaccine that does not resolve to within grade 1 or lower within 8 wks.
- Off Treatment- Severe or life-threatening immediate hypersensitivity reactions following receipt of quadrivalent HPV vaccine.
- Off Treatment and Off Study- Development of an acute life-threatening condition or cancer.
- Off Treatment and Off Study- Inability to adhere to HAART.
- Off Treatment and Off Study- Discontinuation of HAART for >6 wks due to antiretroviral toxicity.
- Off Treatment- > 30% decrease in baseline CD4 cell count or percent or decrease in absolute CD4 count to < 350 cells/mm³ confirmed by at least 2 measurements 4 weeks apart.
- Off Treatment- Increase in HIV-1 RNA levels to > 100,000 copies/ml confirmed by at least 2 measurements 4 weeks apart.
- Off Treatment- Pregnancy. Patients will be taken off-study and advised to defer completion of their vaccination regimen until resolution of the pregnancy. Patients will also be reported to the Merck Pregnancy Registry [contact]) that monitors fetal outcomes of pregnant women exposed to GARDASIL®.
- Off Study- Non-compliance with study protocol evaluations and visits.
- Off Study- Study discontinuation at the request of the patient or at the discretion of the Principal Investigator or Lead Associate Investigator if they determine that study withdrawal is in the patient's best interest.

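### The count-based virologic stopping rule (6.7) can only halt accrual, so if the count is reached after enrolment closes the rule requires no action

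*Combined protocol and SAP*

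**What the plan says.** Section 6.7 (Accrual Stopping Rule) sets two limits. The first is "Accrual to the HIV-infected cohorts (Cohort 1 and Cohort 2) will be halted if 3 or more patients within a given cohort"; the second is "5 or more total patients between the two cohorts are removed from the study before month 12". The countable reasons for removal are a CD4 decline and/or a rise in HIV-1 RNA.

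The paragraph says that these events before month 12 would be "suggestive of potential excess virologic safety risk possibly related to HPV vaccination", and puts later events down to antiretroviral resistance or natural history. It says month 12 was chosen "as it includes 12 months of observation following the first HPV vaccination and 6 months of observation following completion of the vaccination series".

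The follow-on step is: "In the event that accrual to the study is halted, the IRB will be consulted to determine whether the halt on enrollment should be permanent". The alternative put to the IRB is that a protocol amendment could deal with the matter. Nothing is said about the count being reached when no accrual remains to be halted.

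The Precis gives the size and schedule: "Each cohort will enroll 35 patients", with "three doses of HPV vaccine at 0, 2 and 6 months administered IM".

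**The concern.** The rule detects a pattern across patients that the protocol itself regards as a possible harm of vaccination, yet its only response is to stop new patients entering. The events it counts accrue over 12 months per patient, and the 3.7 criteria need confirmation by measurements 4 weeks apart. Part of the evidence therefore arrives after the last patient has enrolled. At that stage there is nothing to halt, so the condition for IRB consultation is not met. Some HIV-infected participants could then still have second or third doses to come.

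Section 7.5.1 declines both a DSMB and a single independent monitor, so no outside body would pick up the same count by another route.

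**Working it through.** **1. What else responds to a pattern of CD4 or HIV-1 RNA removals?**

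- Section 3.7 acts on one patient at a time, for example: "Off Treatment- Increase in HIV-1 RNA levels to > 100,000 copies/ml confirmed by at least 2 measurements 4 weeks apart". It has numeric limits and applies whether or not accrual is open, but it does not look across patients.
- Section 7.5.1 provides at least monthly review by the investigator, with no count and no prescribed action. Its item on viral replication concerns Days 1, 3 and 7 after the first dose.
- Section 7.3.1 sends unanticipated problems to the IRB within 7 days. Whether an event qualifies is a judgement under the definition in 7.1.10.
- Section 7.4.4 sends adverse vaccine reactions to the IRB, the FDA and the manufacturer within 10 working days, again by judgement.

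None of these is triggered by 3 in a cohort or 5 in total. Section 6.7 is therefore the only aggregate count threshold, though not the only safety provision.

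**2. How much of the window falls after closure?**

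The plan states no figure to reproduce: no accrual period, error rate or operating characteristic is given for the rule. Its timing is consistent (12 − 0 = 12 months after dose 1; 12 − 6 = 6 months after dose 3).

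Inputs from the documents: 35 patients in each of Cohorts 1 and 2 (70 in all), a 12-month counting window, and the last dose at month 6. Assumed: even accrual over T months, both cohorts closing together, and no dropout. A patient enters at time u, uniform on (0, T).

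- Share of the first 12 months before closure = mean of min(12, T − u)/12. This is T/24 for T ≤ 12 and 1 − 6/T for T ≥ 12. The share after closure is 1 minus this.
- Post-closure time with a dose pending = mean of max(0, u + 6 − T). For T ≥ 6 this is (1/T) × 6²/2 = 18/T months per patient, or 1.5/T of the 12-month window.
- Patients with dose 3 still to come at closure = 70 × min(1, 6/T).

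| Assumed T (months) | First 12 months after closure | Post-closure with a dose pending | Patients with dose 3 to come at closure |
|---|---|---|---|
| 6 | 1 − 6/24 = 75% | 3.0/12 = 25% | 70 |
| 12 | 1 − 12/24 = 50% | 1.5/12 = 12.5% | 35 |
| 24 | 6/24 = 25% | 0.75/12 = 6.25% | 17.5 |
| 36 | 6/36 = 17% | 0.5/12 = 4.2% | 11.7 |

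Whatever T is, the last-enrolled patient's whole 12 months, and doses 2 and 3, fall after closure.

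**3. How often would the count be reached too late?**

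With two cohorts, 5 in total implies at least 3 in one of them, so only the per-cohort limit matters. The chance of ever meeting it is 1 − (1 − P)², where P = P(≥3 of 35).

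- At an assumed 5% removal rate: P = 0.254, giving 0.444.
- At an assumed 10% removal rate: P = 0.694, giving 0.906.

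A simulation (20,000 replicates, even entry, event times uniform over months 0 to 12) gives the share of those hits that come after the last enrolment:

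| Assumed T (months) | 5% removal rate | 10% removal rate |
|---|---|---|
| 6 | 96% | 89% |
| 12 | 77% | 54% |
| 24 | 43% | 19% |
| 36 | 29% | 11% |

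These shares are illustrative. Neither the removal rate nor T is in the documents.

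**The case against.** Several counter-arguments have force, and each limits what may be concluded.

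- **A reader might infer that nothing at all happens after enrolment closes, or that the IRB could not be told.** The documents do not support that. Sections 3.7, 7.3.1, 7.4.4 and 7.5.1 continue to apply, and 6.7's own description of the events comes close to the definition of an unanticipated problem. What stands is that these routes depend on judgement or act on one patient, and the count does not set them off.
- **A reader might call 6.7 the only numeric safety boundary.** It is not: 3.7 contains numeric CD4 and HIV-1 RNA limits. It is the only one that counts across patients.
- **A reader might take the month 12 rationale as a promise that the halt stays active for 12 months.** It is better read as an attribution cutoff deciding which events count. The section is titled and built as an accrual rule. This is a gap, not a contradiction.
- **A reader might conclude that the IRB is barred from considering enrolled participants.** The question put to it includes a protocol amendment, and nothing confines an amendment to enrolment. Those participants are simply not mentioned.
- **The larger percentages cover all time to month 12, not time under vaccination.** That is right. The share with a dose pending is three to four times smaller, so both are shown.
- **Accrual may be slow.** All visits are at one centre, up to 10 replacements are allowed in each HIV-infected cohort (3.3.1), and 6.2 allows expanded enrolment. The rule also stays live while either HIV-infected cohort is still recruiting. All of this shrinks the gap but cannot remove it.

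**Conclusion.** The point holds in this limited form. Followed as written, 6.7 requires no action if its count is reached after enrolment closes, and no other provision is tied to that count. That follows from the text and needs no assumption.

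The size of the gap does rest on assumptions. For even accrual over 6 to 36 months, 75% down to 17% of the first 12 months falls after closure, and 25% down to 4.2% of that window is post-closure time with a dose pending. The largest figures need 70 HIV-infected patients recruited within 6 to 12 months, which the documents neither state nor exclude.

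This is a cheap improvement to a safety provision, not a flaw in the study's primary analyses. The current version is dated January 2019. If every HIV-infected participant is already past month 12, the change has no operational effect, but the documents do not say so.

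**What to change.** Reword 6.7 so that reaching 3 in a cohort or 5 in total itself triggers prompt IRB consultation, whether or not accrual is open. State that the consultation covers participants already enrolled with doses pending, as well as any halt to enrolment. What should happen to those doses is for the sponsor and the IRB; no rule is proposed here.

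The same edit should reconcile two references. Section 6.7 points to 3.9, 3.9.7 and 3.9.8, whereas the criteria stand in 3.7. It also counts patients removed from the study, whereas 3.7 labels the CD4 and HIV-1 RNA criteria as off treatment only.

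The cost is one or two sentences and at most one additional IRB consultation. Sample size, visits and analyses are unchanged.
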